### 12 Suspension or Premature Termination of the Clinical Study

The Sponsor reserves the right to terminate the clinical study at any stage, with appropriate written notice to the investigators, IRB/ECs and relevant Regulatory authorities, if required.

## Clinical Investigation Plan

A Principal Investigator, IRB/EC or regulatory authority may suspend or prematurely terminate participation in a clinical study at the study sites for which they are responsible. The investigators will follow the requirements specified in the Clinical Trial Agreement.

If suspicion of an unacceptable risk to subjects arises during the clinical study or when so instructed by the IRB/EC or regulatory authority, the Sponsor may suspend the clinical study while the risk is assessed. The Sponsor will terminate the clinical study if an unacceptable risk is confirmed. If the Sponsor completes an analysis of the reasons for the suspension, implements the necessary corrective actions, and decides to lift the temporary suspension, the Sponsor will inform the Principal Investigators, IRB/EC, or regulatory authority, where appropriate, of the rationale, providing them with the relevant data supporting this decision. Approval from the IRB/EC or regulatory authority, where appropriate, will be obtained before the clinical study resumes. If subjects have been informed of the suspension, the Principal Investigator or authorized designee will inform them of the reasons for resumption.

If the Sponsor suspends or prematurely terminates the clinical study at an individual study site in the interest of safety, the Sponsor will inform all other Principal Investigators.

If suspension or premature termination occurs, the Sponsor will remain responsible for providing resources to fulfill the obligations from the CIP and existing agreements for following up the subjects enrolled in the clinical study, and the Principal Investigator or authorized designee will promptly inform the enrolled subjects at his/her study site, if appropriate.

### 13 Clinical Study Conclusion

The study will be concluded when:

- All sites are closed AND
- The Final Report generated by SJM has been provided to sites or SJM has provided formal documentation of study closure.

### 14 Publication Policy

Publications or presentations of clinical study methods or results will adhere to SJM's publication policy, which is based on Good Publication Practices and International Committee of Medical Journal Editors (ICMJE) guidelines. A copy of the policy will be provided upon request of the investigator.

Publication planning and authorship determinations will be overseen by the Steering Committee, and investigators will be notified via email about the dissemination of study data and opportunities for involvement as authors on publications/presentations.

### 15 Reporting Results on ClinicalTrials.gov Website

This study will be posted on ClinicalTrials.gov and results will be posted on ClinicalTrials.gov as required.

## Clinical Investigation Plan

### Appendix B: Definitions

#### Non-study Specific Definitions

##### **Adverse Event (AE)**

Any untoward medical occurrence, unintended disease or injury, or untoward clinical signs (including abnormal laboratory findings) in subjects, users or other persons, whether or not related to the medical device under study.

This definition includes events related to the medical device or the comparator.

This definition includes events related to the procedures involved.

##### **Serious Adverse Event (SAE)**

An adverse event that led to:

- Death
- A serious deterioration in the health of the subject, that either resulted in:
  - A life-threatening illness or injury OR
  - A permanent impairment to a body structure or a body function OR
  - An in-patient or prolonged hospitalization OR
  - A medical or surgical intervention to prevent life-threatening illness or injury or permanent impairment to a body structure or a body OR
- A malignant tumor
- Fetal distress, fetal death or a congenital abnormality or birth defect

A planned hospitalization for a pre-existing condition, or a procedure required by the CIP is not considered a serious adverse event.

##### **Adverse Device Effect (ADE)**

An adverse event related to the use of an investigational medical device.

This definition includes adverse events resulting from insufficient or inadequate instructions for use, deployment, implantation, installation, or operation, or any malfunction of the investigational medical device.

This definition includes any event resulting from the use error or from intentional misuse of the investigational medical device.

##### **Serious Adverse Device Effect (SADE)**

Adverse device effect that has resulted in any of the consequences characteristic of a serious adverse event.

#### Study Specific Definitions

##### **EDMUNDS CRITERIA**

##### **Major Bleeding Event**

Any episode of major internal or external bleeding that causes death, hospitalization, operation, pericardiocentesis, or permanent injury (e.g., vision loss) or requires transfusion. A bleeding event is reportable whether or not the subject is taking anticoagulation or antiplatelet drugs, since bleeding events can occur in subjects who are not receiving anticoagulants.

## Clinical Investigation Plan

Embolic stroke complicated by bleeding is classified as a neurological event under “embolism” and is not included as a separate bleeding event.

### Death

Valve-related Mortality: Death due to any of the following events involving the study valve: structural valvular deterioration, nonstructural dysfunction, valve thrombosis, embolism, bleeding event, endocarditis, or reoperation. Sudden, unexplained deaths of subjects with an operated valve are included as valve related mortality.

Sudden, unexpected, and unexplained deaths are sudden when they occur within one hour of an event of abrupt onset; unexpected if they occur in a previously well subject; and unexplained if no cause can be determined.

Other cardiac Mortality: Death resulting from cardiac causes, excluding valve-related mortality. Examples include congestive heart failure, acute myocardial infarction, and documented fatal arrhythmias.

Other cause Mortality: Death due to any cause, excluding valve-related mortality or other cardiac mortality.

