##### Freedom from valve related mortality at 5 years post implant

Kaplan-Meier (KM) estimate and 95% confidence interval will be reported for the freedom from valve related mortality at 5 years post implant. [REDACTED]

[REDACTED]

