## Clinical Investigation Plan

### 8.2.1 Subject Death

All subject deaths are to be documented on the Death Form and reported to the Sponsor as soon as possible after becoming aware of the event.

The subject Death Form should always be accompanied with the relevant Adverse Event Form and relevant source documentation. In the event of a subject death, an autopsy should be performed whenever possible and the Trifecta GT valve explanted and returned to SJM for evaluation. If available, death summaries and autopsy reports should be provided to SJM.

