##### 2.2.3 Survival Analyses

Survival analysis will be conducted to analyze all time-to-event variables. Subjects without events will be censored at their last known event-free time point. Survival curves will be constructed using Kaplan-Meier estimates.

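### The death definitions have no class for undetermined cause, so an unexplained death of unknown timing falls by default to other cause and may flatter freedom from valve-related mortality

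*Protocol*

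**What the plan says.** Protocol Appendix B, under Death, sets up three classes.

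- **Valve-related.** Death from any of a list of events involving the study valve, plus one further group: "Sudden, unexplained deaths of subjects with an operated valve are included as valve related mortality". The terms are then explained: "Sudden, unexpected, and unexplained deaths are sudden when they occur within one hour of an event of abrupt onset". The explanation continues: "unexpected if they occur in a previously well subject; and unexplained if no cause can be determined".
- **Other cardiac.** "Other cardiac Mortality: Death resulting from cardiac causes, excluding valve-related mortality".
- **Other cause.** "Other cause Mortality: Death due to any cause, excluding valve-related mortality or other cardiac mortality".

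The affected endpoint is one of the five descriptive endpoints. Protocol 6.1.2 states: "Kaplan-Meier (KM) estimate and 95% confidence interval will be reported for the freedom from valve related mortality at 5 years post implant". SAP 2.3.2 refers all time-to-event endpoints to SAP 2.2.3, where "Subjects without events will be censored at their last known event-free time point". SAP 2.9 plans no imputation.

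On evidence about cause of death, Protocol 8.2.1 asks for a Death Form with source documents and for an autopsy where possible. It adds: "If available, death summaries and autopsy reports should be provided to SJM". Protocol 5.10.2 provides for an independent CEC, whose charter is not among the documents.

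**The concern.** The third class is defined only by exclusion, so the three classes together cover every death. None of them is meant for a death about which too little is known. The sudden-death rule shows that the plan intends at least some unexplained deaths in valve recipients to count against the valve. An equally unexplained death whose timing is unknown is handled the opposite way, because the one-hour interval cannot be shown.

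Such deaths are foreseeable. After the 1-year visit, scheduled contacts are a year apart, and telephone contact may replace an office visit at years 1, 2 and 4 (Protocol 5.4.4). Autopsies and death summaries will not always be available.

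If some of these deaths are truly valve-related, a named safety result is too favourable, and weaker information on cause of death makes it more so. All-cause mortality is unaffected, but it cannot show how many deaths could not be attributed.

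**Working it through.** **Step 1. Put one case through the definitions.** Take a subject found dead, with no autopsy and no known time of onset.

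1. Death from a listed valve event: not shown.
2. Sudden and unexplained: no cause can be determined, so the death is unexplained. Sudden needs the one-hour interval, which is not established.
3. Other cardiac: needs a cardiac cause, and none is known.
4. Other cause: takes whatever the first two classes exclude. The death lands here.
5. SAP 2.2.3: the subject has no valve-related event and is censored.

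No sensitivity analysis for such deaths is visible in SAP 2.3.2 or 2.9.

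**Step 2. Compare the two sentences on sudden death.** The sentence that brings deaths into the valve-related class names two conditions, sudden and unexplained. The next sentence defines three: sudden, unexpected and unexplained. Unexpected means that the subject was previously well. It is therefore unclear how to class a sudden, unexplained death in a subject who was already ill.

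**Step 3. Size.** The documents give no expected valve-related mortality, and the basis of the sample size is redacted, so there is no plan figure to reproduce. What follows is a sensitivity calculation.

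- From the documents: N = 350.
- Assumed counts over 5 years: valve-related deaths v = 3, 7 or 14; unknown-cause deaths u = 1, 3, 5 or 10; other deaths o and withdrawals w = 0 and 0, 35 and 35, or 50 and 70.
- Model: constant cause-specific hazards.

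Total exits are T = v + u + o + w. The total cumulative hazard is H = −ln(1 − T/N). The expected 5-year Kaplan-Meier estimate is exp(−H × E/T), with E = v if unknown-cause deaths are censored and E = v + u if they count as valve-related.

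Worked example: v = 7, u = 5, o = 35, w = 35.

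- T = 82 and H = −ln(1 − 82/350) = 0.2669.
- Censored: exp(−0.2669 × 7/82) = 97.75%.
- Counted: exp(−0.2669 × 12/82) = 96.17%.
- Difference: 1.58 points, or 1.58/5 = 0.32 points per death.

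Fall in the estimate, in percentage points, when unknown-cause deaths are counted (range over v = 3, 7, 14):

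| Other deaths, withdrawals | u = 1 | u = 3 | u = 5 | u = 10 |
|---|---|---|---|---|
| 0, 0 | 0.28 | 0.84–0.85 | 1.40–1.42 | 2.80–2.84 |
| 35, 35 | 0.31–0.32 | 0.94–0.95 | 1.56–1.59 | 3.12–3.18 |
| 50, 70 | 0.34–0.35 | 1.03–1.05 | 1.71–1.74 | 3.43–3.49 |

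Each reclassified death moves the estimate by about 0.28 to 0.35 points. This is the gap between the two ways of scoring. The bias itself would be the part of that gap due to deaths that were truly valve-related.

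**The case against.** The best defence is that classification is a matter for adjudication. Death is among the Edmunds events listed in Protocol 8.2, and an independent CEC adjudicates events of that kind. A reader might infer from Appendix B that the onset has to be observed. The text does not say so, and nothing stops the CEC from judging an unwitnessed death sudden from its circumstances. The charter may already contain an undetermined class, and redacted text follows the Kaplan-Meier sentence for this endpoint in Protocol 6.1.2. This stands, and it makes the concern conditional. It does not remove it, because the visible definitions give the CEC no direction for this case.

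Second, a reader might infer that everything outside the one-hour rule goes to other cause. That is wrong. Deaths from the listed valve events are valve-related whatever their timing, and known cardiac deaths have their own class. The gap concerns only deaths with no determinable cause that are not shown to be sudden.

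Third, ascertainment is not careless. Office visits are the norm, serious events are due to the sponsor within 3 calendar days of awareness, and the Death Form should always come with source documents. No document gives a rate of unwitnessed deaths, so it cannot be said that such cases will be common.

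Fourth, Appendix B presents these as the published Edmunds criteria. Counting every undetermined death as valve-related in the main result would depart from them and would over-count any such deaths that had nothing to do with the valve. This also stands, and it is why the fix below keeps the main estimate as it is.

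**Conclusion.** The point holds as a gap in the definitions. The three classes are exhaustive, the last is a residual, and a death of unknown cause and unknown timing falls into it on a literal reading. Any resulting error in 5-year freedom from valve-related mortality is upward, since such a death is censored and never counted as an event.

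The two scorings differ by about 0.3 percentage points per death at 350 subjects, under constant hazards and the assumed counts above. The total cannot be estimated, because the documents do not give the number of such deaths.

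A reader might go further and conclude that the endpoint is inflated. The documents do not show that. It would require the CEC to apply the text literally and some of these deaths to be truly valve-related, and neither can be established from what is available.

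The consequence is limited. The endpoint is descriptive, there is no hypothesis test or success threshold, and neither the primary endpoint nor all-cause mortality depends on this classification. This is a cheap improvement.

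**What to change.** - **Protocol Appendix B, Death** (and the CEC charter, if it does not already do so): add an undetermined-cause class for deaths that have no determinable cause and are not shown to be sudden.
- **Same section:** state whether unexpected is a condition of the sudden-death rule, so that the two sentences agree.
- **SAP 2.3.2:** keep the estimate based on the Edmunds definitions as the main result. Add a sensitivity Kaplan-Meier estimate that counts undetermined deaths as valve-related, and report the number of undetermined deaths.

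The cost is a few lines of definition and one extra estimate. That estimate will look less favourable than the main one whenever there are undetermined deaths. Together the two bound the effect of deaths whose cause could not be determined.

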### Embolism

Embolism is any embolic event that occurs in the absence of infection after the immediate perioperative period (when anesthesia-induced unconsciousness is completely reversed). Only arterial emboli will be captured. Pulmonary emboli, cardiac mural thromboemboli and atherosclerotic particle emboli are not to be reported. Subsets of embolic events are:

#### Neurologic Event:

Any new, temporary, or permanent focal or global neurological deficit. Psychomotor deficits determined by specialized testing are not considered neurologic events related to operated valves. Types of neurologic events are:

- Transient Ischemic Attack (TIA): Fully reversible neurologic deficit that lasts less than or equal to 24 hours, and if an imaging study is performed, shows no evidence of infarction.
- Reversible Ischemic Neurologic Deficit (RIND): Fully reversible neurologic deficit that lasts more than 24 hours and less than or equal to three weeks.
- Stroke or permanent neurologic event: A neurologic deficit that lasts more than three weeks, causes death or lasts less than or equal to three weeks with a brain imaging study showing an infarction.

#### Systemic Embolic Event:

An operative, autopsy or clinically documented embolus that produced symptoms from complete or partial obstruction of a peripheral (non-cerebral) artery. Systemic events should be classified as:

- Minor: symptoms resolve completely without medical or surgical intervention
- Major: permanent injury or medical/surgical intervention required
- Fatal: death results as a consequence of the embolism or from related adverse events (less than or equal to 30 days or during the same course of hospitalization)

### Endocarditis

## Clinical Investigation Plan

Valvular endocarditis is any infection involving an operated valve. The diagnosis of operated valvular endocarditis is based on customary clinical criteria including an appropriate combination of positive blood cultures, clinical signs and/or histologic confirmation of endocarditis at reoperation or autopsy. Morbidity associated with active infection, such as valve thrombosis, thrombotic embolus, bleeding event, or paravalvular leak, is included under this category and is not included in other areas of morbidity.

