#### 4.4 Study Population

The intended population for this clinical study is subjects who are indicated for surgical aortic valve replacement per current guidelines and intended to be implanted with a St. Jude Medical Trifecta GT valve with or without the following concomitant procedures:

- coronary artery bypass grafting (CABG)
- supracoronary replacement of ascending aorta
- aortic annulus or root enlargement
- atrial fibrillation ablation
- mitral valve repair
- tricuspid valve repair

Subjects who have had a previous aortic valve replacement or coronary artery bypass graft surgery are eligible for this study.

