### 4.4.2 Exclusion Criteria

1. Subject undergoes a concomitant procedure of mitral or tricuspid valve replacement at the time of the Trifecta GT valve implantation surgery.
2. Subject has contraindication for cardiac surgery.
3. Subject is pregnant. Pregnancy will be assessed by the subject informing the physicians.
4. Subject has active endocarditis (subjects who have previously experienced endocarditis must have two documented negative blood culture results while off antibiotic therapy prior to the valve implantation surgery).
5. Subject has had a stroke or transient ischemic attack within 6 months prior to the planned valve implantation surgery.
6. Subject is undergoing renal dialysis.
7. Subject has a history of active drug addiction, active alcohol abuse, or psychiatric hospital admission for psychosis within the prior 2 years.
8. Subject has a documented thrombus in the left atrium or left ventricle at the time of the valve implantation surgery.
9. Subject has a left ventricular ejection fraction < 30%.
10. Subject previously enrolled in the Trifecta GT PMCF study and withdrawn (a subject cannot be enrolled twice in this study).
11. Preoperative evaluation indicates other significant cardiovascular abnormalities such as aortic dissection or ventricular aneurysm.
12. Subject has a life expectancy less than 2 years.

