### **Nonstructural Dysfunction**

Nonstructural dysfunction is any abnormality resulting in stenosis or regurgitation at the operated valve that is not intrinsic to the valve itself. Nonstructural dysfunction refers to nonstructural problems that result in dysfunction of a study valve *exclusive of thrombosis or infection* diagnosed by reoperation, autopsy, or clinical investigation.

Examples of nonstructural dysfunction include: entrapment by pannus, tissue, or suture; paravalvular leak, inappropriate sizing or positioning, residual leak or obstruction from valve implantation or repair, and clinically significant hemolytic anemia.

Sudden or progressive dysfunction or deterioration of the study valve may be structural, nonstructural, or both as determined by reoperation, autopsy, or clinical investigation.

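### The endocarditis definition covers any operated valve, so infection of a mitral or tricuspid valve repaired at the same operation would enter the adjudicated endocarditis count

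*Protocol*

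**What the plan says.** Protocol 4.4 lists the procedures that may accompany the valve implant. They include "mitral valve repair" and "tricuspid valve repair". The first exclusion criterion in 4.4.2 removes only replacement of those valves: "Subject undergoes a concomitant procedure of mitral or tricuspid valve replacement at the time of the Trifecta GT valve implantation surgery".

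Under Endocarditis, Appendix B opens with "Valvular endocarditis is any infection involving an operated valve". The next sentence, on diagnosis, again refers to the operated valve. The entry then assigns thrombosis, embolus, bleeding and paravalvular leak that accompany active infection to endocarditis, and keeps them out of the other morbidity categories.

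The Nonstructural Dysfunction entry mixes two terms. It begins "Nonstructural dysfunction is any abnormality resulting in stenosis or regurgitation at the operated valve that is not intrinsic to the valve itself", continues "Nonstructural dysfunction refers to nonstructural problems that result in dysfunction of a study valve", and gives "residual leak or obstruction from valve implantation or repair" among its examples.

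Protocol 8.2 lists endocarditis among the reportable Edmunds events, and 5.10.2 has an independent Clinical Events Committee (CEC) adjudicate events of that kind. SAP 3.2 summarizes the CEC-adjudicated events by event count and by the number and percentage of subjects affected.

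**The concern.** The study has a single arm, and its objective is the safety and performance of one aortic valve. A reader will take the adjudicated endocarditis figure as a property of that valve. If the definition also admits infection of a native mitral or tricuspid valve repaired at the same sitting, the figure mixes a device outcome with complications of a permitted concomitant procedure. No control group is present to absorb the difference.

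The rule on associated morbidity extends the problem. An embolus or bleed that accompanies an infected mitral repair would leave its own row and be absorbed into endocarditis. The rest of the appendix mostly uses the narrower term, which suggests that the endocarditis entry was not fully adapted to this study.

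**Working it through.** The documents state no figure for this point, so the check is a comparison of text followed by a simple sizing.

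**1. Which valve each Appendix B entry covers**

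| Entry | Valve named |
|---|---|
| Endocarditis | operated valve throughout; no study-valve limit |
| Valve-related mortality | study valve for the listed causes; operated valve for sudden unexplained death |
| Reoperation | study valve |
| Valve thrombosis | study valve |
| Structural deterioration | study valve in the definition; operated valve only at the end of the list of examples |
| Nonstructural dysfunction | operated valve in sentence 1; study valve in sentence 2 and in the closing paragraph |

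Endocarditis is the only one of these entries with no reference to the study valve.

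**2. A case followed through the rules.** A subject receives a Trifecta GT and a mitral annuloplasty. Later the annuloplasty is infected and an embolus follows; the aortic prosthesis is not involved.

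- Eligibility: allowed by 4.4 and not caught by exclusion 1.
- Endocarditis: the mitral valve is an operated valve, so the definition is met.
- Embolus: the endocarditis entry absorbs it, and the Embolism entry independently requires absence of infection, so it is not counted there.
- Reporting: the case enters the CEC endocarditis count. SAP 3.2 states no split of that summary by valve.

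**3. Reach into the endpoints.**

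- Neither the primary endpoint nor any of the five descriptive endpoints uses endocarditis directly.
- Valve-related mortality includes endocarditis deaths only when the study valve is involved.
- The sudden-death sentence uses the broader term but adds nobody, because every implanted subject has an operated aortic valve.

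**4. Size.** The documents give neither the expected share of subjects with a repair nor an infection rate. The sample size basis and the analysis population are redacted, so the planned 350 serves as denominator.

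- One extra event adds 1/350 = 0.29 percentage points.
- Over an assumed range of 0 to 2 extra events, the addition is 0 to 2/350 = 0.57 points.
- To show what one event implies: if 10% to 20% of subjects had a repair (assumed), that is 35 to 70 subjects. One infection among them is 1/70 = 1.4% to 1/35 = 2.9% over 5 years.

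**The case against.** Several points count on the other side.

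- **Device attribution is separate.** A reader might infer that these infections would be reported as caused by the Trifecta GT. The documents do not support that. Protocol 8.2 requires relationship to device for each event, and SAP 3.2 summarizes adverse events by device, procedure or unrelated. This stands, with two limits. The CEC summary has no stated split by relationship, and the SAP's device-effect categories combine device-related with procedure-related events.
- **Nonstructural dysfunction.** A reader might also infer that residual mitral or tricuspid leaks inflate this category. They do not on a fair reading. The entry's second sentence and closing paragraph restrict it to the study valve, and the mention of repair sits in a list of examples that does not override the restriction. The entry is loosely worded, but no over-count can be shown.
- **Reporting is appropriate.** A serious infection of any heart valve should be reported as a serious adverse event. This is correct; the issue is only which row counts it.
- **Unseen documents.** The CEC charter and the case report form are not available and may already identify the valve. That could remove the practical effect, but sites report from Appendix B, so its text should agree with them.
- **Earlier mitral or tricuspid prostheses.** Exclusion 1 addresses only replacement at the implant operation, so one might argue that subjects with an older prosthesis are a further source. The criteria do not address such a history, and the point does not rely on it.

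**Conclusion.** The concern holds for endocarditis. As written, the definition counts infection of a concomitantly repaired mitral or tricuspid valve, together with its associated emboli or bleeding, in an adjudicated summary that has no stated split by valve.

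The likely size is small, perhaps one event or about 0.3 percentage points. This rests on assumed repair and infection frequencies and cannot be derived from the documents. The effect is confined to a descriptive safety table: there is no hypothesis test, and the primary and descriptive endpoints are not materially affected. It is still worth correcting, because a stated rule would miscount a device safety event in a single-arm study and the correction costs little.

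**What to change.** 1. In the Endocarditis entry of Appendix B, replace the reference to an operated valve with the study valve, defined as the implanted Trifecta GT. Make the diagnostic sentence consistent.
2. Record the valve involved for each adjudicated endocarditis event, and bring the CEC charter into line if it differs.
3. In the SAP 3.2 table of CEC events, list infections of other valves in a separate row. State that their associated emboli, bleeding and thrombosis are reported with that row. Otherwise emboli would appear nowhere, since the Embolism entry excludes infection.
4. In the same edit, change the first sentence of Nonstructural Dysfunction to the study valve, to match its second sentence, and limit the example that mentions repair to the study valve. This is a clarification only.

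The cost is a wording change in Appendix B and, if needed, the charter, plus one data field and one table row. No visits or procedures are added. If events have already been adjudicated, the valve involved would have to be added to those records.
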